## 2 STUDY OBJECTIVES AND ENDPOINTS

OBJECTIVES	ENDPOINTS
Safety	Safety endpoints
To assess the safety of ARQ-151 cream 0.05% vs ARQ-151 cream 0.15% vs vehicle administered QD x 4 weeks to adolescent and adult subjects with mild to moderate atopic dermatitis.	
 
Incidence of local and non-local treatment-emergent adverse events (TEAEs)
 
Change from baseline in vital signs
 
Change from baseline in clinical laboratory test results
 
Change from baseline in electrocardiograms (ECG)
 
Patient Health Questionnaire – 8 (PHQ-8) and Columbia Suicide Severity Rating Scale (C-SSRS) assessments
 
Local tolerability assessments
 
 
Subset analysis by age group (adolescents and adults) will also be conducted.

Efficacy	Efficacy endpoints
To assess the efficacy of ARQ-151 cream 0.05% vs ARQ-151 cream 0.15% vs vehicle administered QD x 4 weeks to adolescent and adult subjects with mild to moderate atopic dermatitis.	
Primary:
 
 
Change from baseline in Eczema Area and Severity Index (EASI) Total Score at Week 4
 

Protocol Number: AQR-151-212

Sponsor: Arcutis, Inc.

	
Secondary:
 

• Percent change from baseline in EASI Total Score at each study visit

• Change from baseline in EASI Total Score at weeks 1 and 2

• Achievement of a 75% or greater improvement in EASI (EASI75) score from baseline to each study visit

• Achievement of a 50% or greater improvement in EASI (EASI50) score from baseline to each study visit

• Change from baseline in BSA involvement at each study visit

• Change from baseline in WI-NRS pruritus score at each study visit

• Achievement of a <math>\geq 4</math>-point improvement from Baseline in WI-NRS pruritus score at each study visit for subjects with a Baseline WI-NRS <math>\geq 4</math>

 
Subset analysis by age group (adolescents and adults) and baseline EASI score ('2' (mild) or '3' (moderate)) will also be conducted.

Pharmacokinetic	Pharmacokinetic endpoints (not covered in this SAP)
To evaluate the systemic exposure and characterize the plasma pharmacokinetic (PK) profile of ARQ-151 cream 0.05% and 0.15% and its major N-oxide metabolite, in adolescent and adult subjects with mild to moderate atopic dermatitis.	

• Plasma levels of circulating roflumilast and its major N-oxide metabolite

• Exposure of roflumilast and its major N-oxide metabolite (as evidenced by the <math>C_{max}</math> and AUC) for subjects who have serial PK data.

 INNOVADERM RESEARCH INC.	STATISTICAL ANALYSIS PLAN, Final V1.0Final 1.0
Protocol Number: AQR-151-212	Sponsor: Arcutis, Inc.

## 3 STUDY DESIGN

---

### 3.1 Overall Design

This is a phase 2, parallel group, double blind, vehicle-controlled study of ARQ-151 cream 0.15% and ARQ-151 cream 0.05% QD applied for 4 weeks to adolescent and adult subjects with 1.5% to 35% BSA of mild to moderate atopic dermatitis. A subset of subjects that consented under the previous amendment will have serial PK testing, while only trough PK sampling will be performed for all new subjects enrolled under protocol amendment 2.0.

A total of up to approximately 90 to 105 subjects will be enrolled at approximately 30 study sites in the United States and Canada. Subjects will be adolescent (12-17 y/o) or adult ( $\geq 18$  y/o) males or females with atopic dermatitis. Subjects must have a VIGA-AD of Mild ('2') or Moderate ('3') at Baseline. Subjects must have at least 1.5% and no more than 35% BSA of atopic dermatitis (excluding scalp, palms, and soles). All atopic dermatitis lesions on a subject will be treated including the face, trunk, genitals/skin folds, or limbs (excluding the scalp). The palms and soles will be treated but will not be counted towards any measurements of efficacy (EASI, BSA).

Subject participation involves a minimum of 5 clinic visits including Screening, Baseline, Week 1, Week 2, and Week 4. For the subset of subjects enrolled under amendment 1.0 and consented to participate in serial PK sampling, 2 additional clinic visits include the 24-hour PK sample collection after Baseline on Day 2 and on Day 16. The interval between the Screening and Baseline visits could be up to 4 weeks, therefore the anticipated maximum duration of subject participation is ~8 weeks.

### 3.2 Schedule of Events

[Table 1](#) provides a description of the procedures planned at each visit.

Protocol Number: AQR-151-212

Sponsor: Arcutis, Inc.

**Table 1: Study Events Flow Chart**

Study Procedure	Screen	Baseline Day 1	Day 2, 24-hour PK Collection	Wk 1 Day 8	Wk 2 Day 15	Day 16, 24-hour PK Collection	Wk 4 Day 29
Visit	1	2	3	4	5	6	7
Visit Window	-4 weeks			+/- 3 days	+/- 3 days		+/- 3 days
Informed consent	X						
Demographics	X						
Medical and surgical history	X						
Physical examination a	X	X					X
I/E criteria	X	X					
Hematology, Serum Chemistries, and Urine Analysis	X	X					X
12 lead ECG	X						X
Vital signs, height, weight b	X	X		X	X		X
vIGA-AD c , EASI c , BSA c	X	X		X	X		X
WI-NRS pruritus d	X	X		X	X		X
Local Tolerability Assessment e		X		X	X		X
PHQ-8, C-SSRS	X	X		X	X		X
Optional photography f		X		X			X
Serum pregnancy test	X						
Urine pregnancy test g		X		X	X		X
PK draws h		X	X		X	X	X
Drug/vehicle application in clinic i		X		X	X		
Dispense study medication kit j		X		X	X		
Dispense/review diary		X		X o	X		X n
Weigh study medication kit k		X		X	X		X
Compliance calculation l		X		X	X		X
Adverse event assessment m	X	X	X	X	X	X	X
Concomitant medications	X	X		X	X		X

a Limited physical examination: skin, lungs, and heart only

b Height will be collected at Screening only. Weight will be collected at all study visits. Subject to void prior to weight being taken. Remove any jackets, outerwear and shoes. Remove any objects of significant weight (i.e. cell phones, wallet, key chains). A 5% weight loss should be reported to the medical monitor.

c vIGA-AD will be a 5-point scale ranging from clear (0) to severe (4) and is evaluated for the entire body except the scalp, palms, and soles. EASI takes into account overall severity of erythema, infiltration/papulation, excoriation, and lichenification, in addition to extent of BSA affected. The 4 clinical signs will be graded on a 4-point scale (0 [absent] to 3 [severe]) for 4 body regions (head and neck, upper extremities, lower extremities, and trunk). Total EASI score will be

Protocol Number: AQR-151-212

Sponsor: Arcutis, Inc.

calculated as a sum of scores of all 4 body regions. EASI total score will range from 0 (absent) to 72 (severe). Total BSA affected by AD will be determined for all body surfaces except the scalp, palms and soles. vIGA-AD should be completed prior to other physician assessments.

- d. Subjects will complete the WI-NRS pruritus questionnaire.
- e. Local tolerability assessments should be recorded prior to study drug application for the Investigator assessment of skin irritation (Berger and Bowman skin irritation score) and 10-15 minutes post-drug application for the subject's '0-3' burning/stinging assessment.
- f. Photography of AD lesion(s) selected by the Investigator will be performed at some investigational sites. Photography will be optional. All efforts will be made to de-identify the subjects.
- g. A urine pregnancy test will be administered to all females of child-bearing potential. A negative result is required for continued participation in the study, and results must be available prior to dispensing of study drug at each visit.
- h. For the subset of subjects who enrolled under the previous protocol amendment and agreed to the serial PK: on the first day of dosing, PK draws will be done pre-dose (within 1-hour) and at 1, 2, 4, 6 (all  $\pm$  20 min) and 24 hours ( $\pm$  2 hr) post-dose administration. On Day 15, PK draws will be taken at pre-dose (within 1-hour), 1, 2, 4, 6 (all  $\pm$  20 min) and 24 hours ( $\pm$  2 hr) post dose administration. For other subjects: PK draws will be collected at Days 1 and 29. The draws will be pre-dose,  $\leq$  60 minutes before drug application in the clinic. Ensure study medication is not applied in the area where PK will be drawn. Note: Day 2 and Day 16 visits for 24-hour PK collection only apply to the subset of subjects who agree to the serial PK.
- i. Subjects to apply assigned IP in clinic at every visit.
- j. Kits will be dispensed based on %BSA affected. See IP Handling Manual for details.
- k. The entire kit should be weighed and recorded at every visit. See IP Handling Manual for details.

 Compliance calculation is described in the IP Handling Manual

m Any emergent AEs will be followed in the clinic for up to one month at the Investigator's discretion until resolved or otherwise judged as clinically stable.

n On Day 29, no further IP will be applied or dispensed.

o On Day 8, dispensing of IP is optional. Site should review IP kit to ensure sufficient IP is available until the next visit and only dispense additional IP if needed.

 INNOVADERM RESEARCH INC.	STATISTICAL ANALYSIS PLAN, Final V1.0Final 1.0
Protocol Number: AQR-151-212	Sponsor: Arcutis, Inc.

### 3.3 Treatment

The treatment groups are:

- ARQ-151 cream 0.05% applied QD (once a day) for 4 weeks
- ARQ-151 cream 0.15% applied QD for 4 weeks
- Matching Vehicle cream applied QD for 4 weeks

### 3.4 Randomization, Replacement, and Unblinding Procedures

#### 3.4.1 Randomization

Subjects will apply ARQ-151 cream 0.15% QD or ARQ-151 cream 0.05% QD or vehicle cream QD. Assignment of drug or vehicle will be made at a 1:1:1 ratio and stratified based on vIGA-AD score of '2' (mild) or '3' (moderate) according to a computer-generated randomization list. Randomization will take place at Baseline after the subject has been found to be fully eligible for participation. Kits containing tubes of study medication will be assigned to each subject using an internet-based response system (IWRS). A subject may receive more than one kit for the treatment period. The kits and tubes are blinded and each kit is numbered with a unique kit number.

This is a double-blind study, therefore neither the subjects nor the Investigator and clinical personnel will be aware of which treatment an individual has received.

#### 3.4.2 Replacement

Subjects that withdraw or are discontinued from the study prior to Final Study Visit, may be replaced.

#### 3.4.3 Unblinding

This is a double-blind study, therefore neither the subjects nor the Investigator and clinical personnel will be aware of which treatment an individual has received until after the database lock. The SAP and the study populations for analysis will be finalized prior to database lock and unblinding occurs.

### 3.5 Changes to the Analysis from the Protocol

The primary method of handling of missing data will be the MMRM method without explicit imputations for missing data as opposed to a multiple imputation technique.

The PHQ-8 scoring in the protocol describes "Severe Depression" as any score between 20 and 27. The PHQ-8 score has a maximum result of 24, The category has been corrected in [section 13.6](#) to a score between 20-24.

 INNOVADERM RESEARCH INC.	STATISTICAL ANALYSIS PLAN, Final V1.0Final 1.0
Protocol Number: AQR-151-212	Sponsor: Arcutis, Inc.

## 4 POPULATIONS FOR ANALYSIS

---

### 4.1 Intent-to-Treat Population

The Intent-to-Treat (ITT) population will include all randomized subjects. All subjects will be analyzed according to the treatment group to which they were randomized, regardless of treatment received.

### 4.2 Per-Protocol Population

The Per-Protocol (PP) Population will include all subjects who are in the safety population, are at least 80% compliant with study medication and do not miss more than 3 consecutive doses, and show no other major deviations (a deviation that affects the interpretation of the primary efficacy outcome; Section 6.6) from the study protocol .

Prior to the database lock, major protocol deviation will be defined and reviewed by the sponsor and the CRO in charge of the study follow-up in a blinded fashion. Subjects with major protocol deviations will be excluded from the PP population.

All subjects will be analyzed according to the actual treatment they received.

### 4.3 Safety Population

The Safety population will include all subjects who are enrolled and received at least one confirmed dose of study medication. Subjects will be analyzed according to the majority of the treatment applications received regardless of the treatment group to which they were randomized.

### 4.4 Pharmacokinetic Population

The PK population will include all subjects with serial PK data, receiving the active drug, with sufficient plasma concentrations of roflumilast and its major N-oxide metabolite to define a profile, as determined by the pharmacokineticist.

## 5 GENERAL CONSIDERATIONS

---

Formats and layouts of tables, listings, and figures (TLF) will be provided in a separate document (output general layout is described in [Appendix 1](#)).

 INNOVADERM RESEARCH INC.	STATISTICAL ANALYSIS PLAN, Final V1.0Final 1.0
Protocol Number: AQR-151-212	Sponsor: Arcutis, Inc.

## 5.1 Sample Size

There are approximately 90-105 subjects planned for this study. A subset of approximately 18 adults will receive serial PK sampling.

Approximately 30-35 subjects will receive ARQ-151 cream 0.05% QD; approximately 30-35 subjects will receive ARQ-151 cream 0.15% QD; approximately 30-35 subjects will receive vehicle QD.

A sample size of 27 per arm will provide at least 80% power to detect a difference in the mean change from baseline in EASI Total Score of 35% at week 4 (for each ARQ-151-treated group versus vehicle-treated group), assuming a pooled standard deviation (SD) of 40%, with a two-sided  $\alpha = 0.05$ . This is based on a 2-sample t-test. This includes P value adjustment for multiplicity using Bonferroni correction. With a 10-25% dropout rate, the sample size for the study would be increased to 30-35 subjects per arm (90-105 subjects total).

Change from baseline in EASI Total Score at week 4 is expected to provide more statistical power than percent change from baseline in EASI Total Score at this timepoint (which is a secondary endpoint) and has been chosen as the primary endpoint.

This sample size is considered adequate for PK and safety evaluation.

## 5.2 Baseline

Unless otherwise specified, baseline value will be defined as the last non missing assessment prior to or on the first study treatment dose date (including unscheduled assessments). If the last non missing assessment is performed on the same date as the first study treatment and time is not available, the assessment will be considered as baseline, except for adverse events (AEs) and medications starting on the first study treatment dose date which will be considered post-baseline.

## 5.3 Reference Start Date and Analysis Day

Analysis day will be calculated from the first study treatment date (day 1) and will be used to show start/end day of assessments or events.

In the situation where the assessment/event date is partial or missing, Analysis day will be missing.

## 5.4 Windowing Conventions

Statistical Windows have been proposed for early termination (ET) visits in this study:

	Day 1 (Baseline)	Day 8	Day 15	Day 29
--	------------------	-------	--------	--------

 INNOVADERM RESEARCH INC.	STATISTICAL ANALYSIS PLAN, Final V1.0Final 1.0
Protocol Number: AQR-151-212	Sponsor: Arcutis, Inc.

Visit	1	4	5	7
Statistical Window	Latest pre-dose measurement	[Day 2; day 11]	[Day 12 – Day 21]	[Day 22 – D32]

If there is more than one assessment for a given timepoint and analysis visit, the assessment closest to the target day will be considered. If there is more than one assessment with the same target date, then the scheduled assessment result will be considered.

## 5.5 Descriptive Statistics

All continuous variables will be summarized by presenting the number of subjects, mean, SD, median, minimum, and maximum. Categorical variables will be presented as frequencies and percentages. Summary tables will be presented by treatment and visit, when applicable.

Change from baseline will be calculated as:

Assessment value at post-baseline visit X – Baseline value.

Percent change from baseline will be calculated as:

(Assessment value at post-baseline visit X – Baseline value) / Baseline value \* 100.

## 5.6 Handling of Retests, Unscheduled Visits, and Early Termination Data

When retests measurements are done, the retest measurement will be considered for the summary analysis. All data from retest visits will be listed.

Unscheduled measurements will not be summarized in by-visit summary tables or figures. However, they will be included in shift summary tables. All data from unscheduled visits will be listed.

Early Termination (ET) visit assessments will be re-mapped according to the windowing conventions in section 5.4.

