10.1.1 Screening

Within 4 weeks prior to the first dosing, subjects will be provided details of study requirements and sign an informed consent. Medical history and demographic data including sex, age, race, ethnicity, body weight (kg), and height (cm) will be recorded. Each subject will undergo atopic dermatitis assessments, a physical examination, ECG, vital sign measurements (blood pressure, heart rate, and temperature) and laboratory tests: hematology, chemistry, urinalysis and a pregnancy test for female subjects of child bearing potential. Abnormal or questionable serum chemistry tests may be repeated at the discretion of the Investigator.

All screened subjects will receive a screening number and be entered into the study tracking document.

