10.1.5 Laboratory Tests

All tests listed below will be performed as follows:

Screening, Baseline, and Week 4.

All tests listed below will be performed according to the Study Events Flow Chart unless otherwise noted. The collection of specimens will be in a non-fasting state (no food restrictions). In addition, laboratory safety tests may be performed at various unscheduled time points, if deemed necessary by the Investigator.

Hematology

- Hemoglobin
- Hematocrit
- Total and differential leukocyte count
- Red blood cell count with indices and morphology
- Platelet count

Serum Chemistry

- Blood Urea Nitrogen
- Bilirubin (total and direct)
- Alkaline phosphatase
- Aspartate aminotransferase
- Alanine aminotransferase
- Albumin
- Sodium
- Potassium
- Chloride
- Glucose
- Creatinine

Urinalysis

- pH
- Specific gravity
- Protein*
- Glucose
- Ketones
- Bilirubin
- Blood*
- Nitrite*
- Urobilinogen
- Leukocyte esterase*

Additional Tests

- Urine pregnancy test**
(for females of child bearing potential only)
- Serum pregnancy test (hCG)***
- FSH test, if indicated

* If urinalysis is positive for protein, blood, nitrite and/or leukocyte esterase, a microscopic examination (for red blood cells, white blood cells, bacteria, casts, and epithelial cells) will be performed.

** At baseline, Week 1, Week 2, and Week 4 for FOCBP only

*** At screening only

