10.6 Unscheduled Visit

Unscheduled visits may be necessary to repeat testing following abnormal laboratory results, for follow-up of AEs, or for any other reason, as warranted in the judgement of the Investigator.

The following information will be collected for all subjects:

- Concomitant medications/procedures
- AEs

The following information also will be collected:

- vIGA-AD and EASI
- BSA affected with AD
- Local tolerability assessment

The rules for how to tally vIGA-AD, BSA or other proportions of categorical responses will be described in the Statistical Analysis Plan.

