10.9 Treatment Stopping Rules

If a subject has non-cutaneous adverse events of concern, clinically significant laboratory values or any condition that the investigator determines could possibly be related to the study drug, the Investigator should immediately contact the Medical Monitor to discuss if the subject should be discontinued from the study.

Treatment for any individual subject will be discontinued if the subject:

- Experiences a serious adverse event (SAE) or a clinically significant non-serious AE which in the opinion of the Principal Investigator or Medical Monitor warrants discontinuation from the study for that subject's well-being.
- A severe (Grade 3) laboratory abnormality (confirmed by repeat sample and considered related to study drug).

Dosing of study drug for an individual subject may be suspended for safety concerns other than those described above, at the discretion of the investigator if he/she feels the subject's safety may be threatened.

A subject with a PHQ-8 score of '15' or above should be referred promptly to a mental health care professional and consideration be given to discontinuation from study drug.

A subject that is experiencing suicidal ideation and behavior should be referred immediately to a qualified mental health care provider and consideration given to discontinuation from study drug.

As noted above, study treatment must be discontinued immediately in the event of a female subject's pregnancy.

Treatment should be interrupted:

- If a subject develops an application site reaction with the clinical appearance of an 'irritation reaction', and with a severity of a Dermal Response Score of 5 (erythema, edema and papules) or greater on the scale of Berger and Bowman, treatment should be interrupted for up to one week and may then be resumed if the reaction has, in the opinion of the Investigator, adequately resolved.

Treatment should be discontinued:

- If the reaction reoccurs, treatment should be discontinued permanently, and the subject followed until the reaction resolves.

For cases of suspected allergic contact dermatitis, the medical monitor and sponsor should be notified and there should be discussion about performing patch testing to further evaluate. Patch testing is encouraged in such cases.

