## 13.2 Clinical Laboratory

Descriptive statistics will be presented for data related to chemistry, hematology, and urinalysis. Change from baseline values will be presented for each post-baseline assessment. Frequencies and percentages for each result will be provided for qualitative urinalysis data.

Shift tables from baseline to the worst post-baseline assessment describing shifts to abnormality will be provided as well. Only subjects with a baseline result and a post-baseline result for the parameter will be considered.

Separate listings of all data for chemistry, hematology, urinalysis, and pregnancy tests will be provided.

Laboratory data will be presented in SI units.

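### SAP 5.6 lets a retest stand in for a valid Week 4 laboratory value; because repeats follow abnormal results, by-visit laboratory summaries lean toward normal

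*SAP*

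**What the plan says.** SAP 5.6 gives the rule in one sentence: "When retests measurements are done, the retest measurement will be considered for the summary analysis". It does not define a retest, restrict the rule to faulty samples, or mention averaging. It then adds: "All data from retest visits will be listed". The next paragraph of 5.6 keeps unscheduled measurements out of by-visit tables and figures but admits them to shift tables.

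The protocol says when tests are repeated. Section 10.6: "Unscheduled visits may be necessary to repeat testing following abnormal laboratory results, for follow-up of AEs, or for any other reason". Section 10.9 refers to a Grade 3 laboratory abnormality that a repeat sample has confirmed. Section 10.1.5 adds that "laboratory safety tests may be performed at various unscheduled time points, if deemed necessary by the Investigator". Scheduled laboratory draws are at Screening, Baseline and Week 4 only.

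SAP 13.2 plans descriptive statistics and change from baseline for laboratory data, with result frequencies for qualitative urinalysis. It continues: "Shift tables from baseline to the worst post-baseline assessment describing shifts to abnormality will be provided as well". SAP 5.4, introduced for early termination visits, takes the assessment nearest the target day and prefers the scheduled one on a tie.

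**The concern.** A rule that replaces one measurement by another is harmless if the choice of whom to remeasure is unrelated to the result. Here it is related. The specific laboratory trigger in Protocol 10.6 is an abnormal result, and no section calls for repeating normal values. Flagged values are therefore exchanged for new ones that tend to lie nearer the centre, by regression to the mean, while unflagged values stay as they are.

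Timing adds a second problem. Week 4 is the only scheduled post-baseline draw, and the schedule footnotes say no study drug is applied on Day 29. A repeat of an abnormal Week 4 sample taken at a later visit may therefore reflect the subject after treatment has stopped, so a reversible drug effect could be lost as well as noise.

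Safety is part of the first primary objective (Protocol 8.1.1), and the laboratory comparison rests on descriptive tables.

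**Working it through.** The documents give no retest frequency, within-subject variability or expected bias, so there is no planned figure to reproduce. The check compares the passages and then sizes the effect under stated assumptions.

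**Which outputs are exposed.** SAP 5.5 defines the continuous summaries as n, mean, SD, median, minimum and maximum. With 13.2, the exposed by-visit outputs are these statistics, change from baseline, and the urinalysis frequencies. The shift tables use the worst post-baseline value, so an abnormal original still counts there if it remains eligible. The SAP does not say whether it does.

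**Whether the rules agree.** Protocol 10.6 places repeat testing after an abnormal result under unscheduled visits. The second paragraph of SAP 5.6 would then keep the repeat out of the by-visit table, while the first paragraph uses it. SAP 5.4 would take the scheduled result on a tie. Two programmers could build different Week 4 tables from the same text.

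**Size for means.** Assumptions, none from the documents:
- the laboratory value is standardised and normal with SD 1; mean μ is 0 on vehicle and 1 on active;
- the upper limit c is 1.96, and only values above it are retested;
- a fraction f of those is retested, and the retest replaces the original;
- the retest has the same mean and SD and correlation ρ with the original (so no loss of drug effect off treatment).

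Each arm's mean falls by f(1−ρ)φ(c−μ), where φ is the standard normal density.
- Active: φ(0.96) = 0.2516.
- Vehicle: φ(1.96) = 0.0584.
- Difference in means after replacement = 1 − f(1−ρ)(0.2516 − 0.0584) = 1 − 0.1932·f(1−ρ).

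| ρ | f | Difference (SD) |
|---|---|---|
| 0.6 | 1 | 1 − 0.0773 = 0.92 |
| 0.8 | 1 | 1 − 0.0386 = 0.96 |
| 0.6 | 0.25 | 1 − 0.0193 = 0.98 |
| 0.8 | 0.25 | 1 − 0.0097 = 0.99 |

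**Size for extremes.** With no drug effect, P(retest > 1.96 given original > 1.96) is 0.249 at ρ = 0.6 and 0.439 at ρ = 0.8, so 75% or 56% of retested high values come back in range. With the 1 SD shift the probabilities are 0.0787/0.1685 = 0.467 and 0.105/0.1685 = 0.623, so 53% or 38% do.

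**Simulation check.** This used two-sided limits of ±1.96, ρ from 0.5 to 0.9, and 25% to 100% of abnormal values retested.
- No true shift: the SD falls from 1.000 to between 0.910 and 0.995. The mean does not move, because the limits are symmetric.
- True shift of 0.5 SD: the mean falls to between 0.442 and 0.497.
- Taking the worse of original and retest leaves the share abnormal unchanged (5.0% with no shift, 7.9% with the 0.5 SD shift). This is why the shift tables are safe if originals stay eligible.

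**The case against.** The strongest reply is that replacement may never happen. Repeat-testing visits are unscheduled under Protocol 10.6, unscheduled values are kept out of by-visit tables, and SAP 5.4 leans to the scheduled result. This stands as evidence of ambiguity. It does not remove an explicit sentence saying the retest is used; it contradicts it.

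A second reply is that little is lost. Laboratory data and retests are listed, SAP 13 plans no formal inference on safety, and the primary endpoint, alpha and power do not involve laboratory values. All of that stands. It is also true that some retests correct a faulty sample, where replacement is proper, and that repeats are partly discretionary, so retesting every high value is an upper bound.

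Three stronger readings are tempting and should not be drawn.
- A reader might infer that reported abnormality rates would be roughly halved. In the model above with every high value retested, the active-arm share above the limit does fall from 16.9% to 7.9-10.5%, and the gap to vehicle from 14.4 to 7.3-9.4 percentage points. But no by-visit abnormality rate is planned for chemistry or hematology. Abnormality appears there in worst-value shift tables, which admit unscheduled values, and no section says originals are deleted. These percentages describe no planned chemistry or hematology table.
- A reader might add Protocol 10.1.1, "Abnormal or questionable serum chemistry tests may be repeated at the discretion of the Investigator", as further support. That sentence concerns screening. Laboratory tests are drawn again at Baseline, and SAP 5.2 takes the last value up to first dose, so a repeated screening value is normally superseded and says nothing about post-baseline bias.
- A reader might treat every change from baseline as shrunk. A pre-dose repeat can itself become the baseline under SAP 5.2, so the net effect for a given subject can go either way.

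**Conclusion.** The point holds for by-visit laboratory summaries. Followed as written, SAP 5.6 replaces valid, flagged Week 4 values and pulls the maximum, SD, mean, change from baseline and urinalysis frequencies toward normal, possibly with off-treatment values. The loss in mean difference is small: about 4-8% of a 1 SD shift if every high value is retested, and about 1-2% if 25% are, at correlations of 0.6 to 0.8. Extremes are affected more. Correlation, shift and retest fraction are assumptions; the direction follows from selective retesting. The normal model does not size the urinalysis frequencies or any off-treatment loss. Shift tables are unaffected only on the condition, which the SAP leaves unstated, that originals remain eligible as the worst value. The conflict within 5.6, and between 5.6 and 5.4, exists whatever the size.

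**What to change.** In SAP 5.6:
- define a retest;
- use the original scheduled value in by-visit summaries unless it is documented as invalid (for example haemolysed or mislabelled), in which case use the retest;
- state that valid originals and retests both count toward the worst post-baseline value in shift tables.

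Then align SAP 5.4 with 5.6, so that one rule settles which of several values represents a visit, and say how a repeat taken at an unscheduled visit is classed. The cost is SAP wording and the matching programming specification. No new data or analyses are needed.
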